9.4.5 PLANNED INTERIM ANALYSES

Interim efficacy analysis will be performed when 24 patients have completed the trial.

If the efficacy pre-specified criteria are fulfilled, the trial will be stopped for overwhelming efficacy. These pre-specified criteria are:

- The average increase in the total UMSARS score is 4 points or less from baseline to week 48 in patients taking active agent – OR –

- The average increase in the total UMSARS score from baseline to week 48 in patients taking active agent is significantly lower than in patients taking placebo with a $P < 0.001$.

If the futility pre-specified criteria are fulfilled the trial will be stopped for futility. These pre-specified criteria are:

- The average increase in the total UMSARS score is at least 7 points or more from baseline to week 48 in patients taking active agent - OR –
- The average increase in the total UMSARS score from baseline to week 48 in patients taking active agent is significantly higher than in patients taking placebo with a $P < 0.001$.

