4.4 END OF STUDY DEFINITION

A participant is considered to have completed the study if he or she has completed all phases of the study including the last visit or the last scheduled procedure shown in the Schedule of Activities (SoA), Section 1.3.

The end of the study occurs when the following circumstance have ALL occurred:

1. Completion of the last visit or procedure shown in the SoA in the trial globally.
2. Completion of data analysis
3. Completion of final study report

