7.2 PARTICIPANT DISCONTINUATION/WITHDRAWAL FROM THE STUDY

Participants are free to withdraw from participation in the study at any time upon request. An investigator may discontinue or withdraw a participant from the study for the following reasons:

- Pregnancy
- Significant study intervention non-compliance
- If any clinical adverse event (AE), laboratory abnormality, or other medical condition or situation occurs such that continued participation in the study would not be in the best interest of the participant
- Disease progression which, in the opinion of the investigator, requires discontinuation of the study intervention
- If the participant meets an exclusion criterion (either newly developed or not previously recognized) that precludes further study participation
- Participant unable to receive study drug for 15 days or more.

The reason for participant discontinuation or withdrawal from the study will be recorded on the electronic Case Report Form (CRF). Subjects who sign the informed consent form and are randomized but do not receive the study intervention may be replaced. Subjects who sign the informed consent form, and are randomized and receive the study intervention, and subsequently withdraw, or are withdrawn or discontinued from the study, will not be replaced.

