9.3 POPULATIONS FOR ANALYSES

Analyses will be performed according to the intention-to-treat principle and will include all randomized subjects who have completed, at least, 3 months of study drug.

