9.4.2 ANALYSIS OF THE PRIMARY EFFICACY ENDPOINT

The primary outcome endpoint (UMSARS total score) will be analyzed by comparing the mean decline in total UMSARS score in the active sirolimus group (UMSARS total score at week 48 minus UMSARS total score at baseline) with the pre-specified fixed value of 8.6 (SD: 9.2) using a one-sample t-test. If the difference between the fixed value of 8.6 minus the UMSARS total score in the active sirolimus group is 4 or less, the null hypothesis will be rejected, indicating futility.

Missing data will be addressed by using a regression-based multiple imputation model (78)

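### The interim stopping rule (9.4.5) is triggered by a count of completers and names no analysis set or missing-data rule, so informative withdrawal could bias the deciding mean downward

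*Combined protocol and SAP*

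**What the plan says.** Section 9.4.5 sets the timing: "Interim efficacy analysis will be performed when 24 patients have completed the trial". The first efficacy criterion is "The average increase in the total UMSARS score is 4 points or less from baseline to week 48 in patients taking active agent". The first futility criterion is that the average increase "is at least 7 points or more from baseline to week 48 in patients taking active agent". Both are raw means set against a fixed limit. Each has an alternative criterion comparing the arms at P < 0.001. The section does not say whose scores enter the mean, or what happens when a week-48 score is missing.

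Four other sections bear on this:

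- Section 4.4 defines completion by study phases and visits: "A participant is considered to have completed the study if he or she has completed all phases of the study including the last visit". Staying on drug is not part of the definition.
- Section 7.2 lists reasons for which an investigator may discontinue or withdraw a participant from the study. One is "Disease progression which, in the opinion of the investigator, requires discontinuation of the study intervention".
- Section 9.3 says that analyses "will include all randomized subjects who have completed, at least, 3 months of study drug".
- Section 9.4.2, for the primary endpoint, says "Missing data will be addressed by using a regression-based multiple imputation model".

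**The concern.** The interim can end the trial, so the set of people who supply its mean needs to be fixed beforehand. Followed as written, 9.4.5 waits for 24 completers and then averages baseline-to-week-48 changes. Only someone with a week-48 score can supply such a change, and the section has no imputation step. A participant withdrawn from the study before week 48 would then be missing from the mean, and a later-enrolled completer would help fill the count of 24. In the primary analysis the same participant, if on drug for at least 3 months, would be included with an imputed score.

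If those who leave tend to be progressing faster, the observed mean is too low for reasons unrelated to sirolimus. An ineffective drug is then more likely to meet the efficacy rule and less likely to meet the futility rule. In a futility trial that is the costly direction of error, and after a stop at this look no final analysis of the full sample follows to correct it. The two between-arm criteria have the same gap, but there the bias depends on leaving that differs between arms.

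**Working it through.** **The plan's figures.** The plan states no operating characteristics for the interim rule. Its benchmark can be checked: (96 × 7.5 + 50 × 10.8)/146 = 8.63 and, weighting the SDs by n, (96 × 8.4 + 50 × 10.7)/146 = 9.19. These agree with the stated 8.6 (SD 9.2).

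**Inputs from the plan.** Limits of 4 and 7 (9.4.5); mean 8.6 and SD 9.2 (9.2, 9.4.2); dropout 10% (9.2); allocation 3:1.

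**Assumptions.** Of 24 completers, 24 × 3/4 = 18 are on sirolimus. The drug has no effect, and 8.6 is the true mean among all randomised. Changes are normal. Leaving depends on a latent normal tendency that has correlation r with UMSARS change.

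**No selection.** SE = 9.2/√18 = 2.168.

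- P(mean ≤ 4) = Φ((4 − 8.6)/2.168) = Φ(−2.12) = 1.7%
- P(mean ≥ 7) = 1 − Φ((7 − 8.6)/2.168) = 1 − Φ(−0.74) = 77%

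**Selection with 10% leaving.** The cut-off is c = 1.2816 and λ = φ(c)/0.9 = 0.1755/0.9 = 0.195.

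- Mean among those who stay = 8.6 − 9.2 × r × 0.195
- SD among those who stay = 9.2 × √(1 − r² × 0.195 × (0.195 + 1.2816))
- Implied mean among leavers = 8.6 + 9.2 × r × 0.1755/0.1

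| r (assumed) | Mean, stayers | SD, stayers | Mean, leavers | P(≤ 4) | P(≥ 7) |
|---|---|---|---|---|---|
| 0 | 8.60 | 9.20 | 8.6 | 1.7% | 77% |
| 0.3 | 8.06 | 9.08 | 13.4 | 2.9% | 69% |
| 0.5 | 7.70 | 8.86 | 16.7 | 3.8% | 63% |

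**Do 9.3 and 9.4.2 close the gap if carried over to the interim?** At the 3 patients per month expected in section 5.5, the 24th participant enrols at about month 8 and has the last scheduled visit (Day 365) at about month 20. Ignoring dropout, those enrolled by month 17, about 17 × 3 = 51, would then have 3 months of drug. Only those enrolled by about month 9, about 27, would have reached week 48. Applying 9.3 literally would mean imputing about 24 of 51 scores for people still on study. If accrual takes the full 24 months (56/24 = 2.33 per month), the same steps give about 45 with 3 months of drug and 26 at week 48, so about 19 imputed. Using the synopsis wording on the last available date instead would mix shorter follow-up with 48-week changes. Section 9.4.5 chooses none of these.

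**The case against.** The case against is substantial, and most of its textual points stand.

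- **The trigger sets timing.** A reader might infer that 9.4.5 restricts the mean to the 24 completers. No sentence says so. That leavers are omitted follows from needing a week-48 score with no imputation stated.
- **The reference to taking active agent is an arm label.** Sections 6.3 and 9.2 use the same phrase for the sirolimus group. A reader might infer an on-treatment restriction, but the documents do not support one.
- **Stopping drug is not leaving the study.** Under 4.4 a participant who stops drug and attends the visits is a completer. Section 7.1 keeps such participants in the study, and section 4.1 asks for 12 months of follow-up, including after withdrawal for an adverse event. The concern is therefore confined to people with no week-48 visit.
- **The final set is not everyone randomised.** Section 9.3 itself drops those with under 3 months of drug, so it would be wrong to contrast the interim with a full intention-to-treat analysis.
- **Direction and size are assumed.** Progression is one of six listed withdrawal reasons. Section 5 says later-stage patients progress only modestly, so leavers need not be the fastest progressors. If the 8.6 benchmark was itself measured in people seen at 12 months, a no-effect mean among completers may already be near 8.6, and much of the shift disappears.

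What does not stand is that 9.3, imputation and the last available date already settle the matter. None is tied to the interim, and each gives a different, awkward result there.

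**Conclusion.** The point holds as a gap in specification with a likely direction of bias. The plan does not fix who decides the interim. On the natural reading, participants who leave the study before week 48 do not count.

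At the plan's own dropout rate and a moderate assumed correlation the effect is modest. The false efficacy stop goes from 1.7% to about 3 or 4%, and the correct futility stop loses 8 to 14 percentage points (77 − 69 and 77 − 63). A reader might reach much larger inflation by assuming heavier withdrawal or much faster progression among leavers, but the documents give no dropout figure above 10% in the sample-size section and nothing on how leavers progress. The result rests on 18 sirolimus participants, normality, 8.6 being the mean for all randomised, and a correlation above zero. The change is still worth making, because the look can end the trial and the remedy works under any reading.

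**What to change.** In 9.4.5, replace the completer count with a fixed cohort: the first 24 randomised and treated participants, analysed once each has reached the week-48 date, died or withdrawn. Then state that:

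1. they are analysed by randomised arm, whether or not still on drug;
2. week-48 scores obtained off drug are used;
3. missing week-48 scores are imputed by the 9.4.2 method, using the month 3, 6 and 9 UMSARS already in the schedule;
4. the cohort's relation to the 3-month condition in 9.3 is set out, so that the interim and final sets agree;
5. all four criteria refer to participants randomised to sirolimus or to placebo, in place of the wording about taking each.

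The cost is a short amendment to 9.4.5, with a matching sentence in 9.3, and a few imputed values: at 10% dropout, about 0.10 × 18 = 1.8 of the sirolimus scores. There should be no material delay, since the 24th treated participant reaches the week-48 date no later than the 24th completer does.

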4 STUDY DESIGN

4.1 OVERALL DESIGN

To determine whether to test sirolimus in a large phase 3 trial, we propose to conduct a clinical trial of sirolimus in MSA using a futility design. A futility design under the null hypothesis assumes that sirolimus will slow the progression of the disease, whereas the alternative hypothesis assumes no benefit of sirolimus. If the null hypothesis is rejected (i.e., futility of sirolimus to slow progression of MSA), major phase 3 studies will be discouraged, whereas non-futility will offer strong support for a phase III trial to detect clinical efficacy.

To test this hypothesis we will perform a single-center, randomized, double blind, placebo-controlled, phase-II, futility trial, chosen as an efficient approach to determine if sirolimus would be worthy of future investigation in larger, more definite trials. This trial was designed to compare the mean value for the primary outcome measure, change in total Unified Multiple System Atrophy Rating Scale (UMSARS) score from baseline to week 48, between the sirolimus arm and a pre-specified fixed value, representing a 4-point reducing in the expected mean decline without treatment; this fixed value was obtained using data from previously completed a large natural history study(39) and the placebo arm of a recently completed clinical trial in MSA (40). The 4-point reduction was based on the recently reported minimally clinically important decline (MICD) in the total UMSARS score of 3.5-points (38).

The null hypothesis is that sirolimus will reduce the mean decline in the total UMSARS score over 12 month by, at least 4-points, compared with the expected (fixed) value obtained from the historical controls. If the null hypothesis is rejected, then the drug would be considered futile for further investigation in MSA. If the null hypothesis is not rejected, sirolimus would be considered for a phase 3 clinical trial.

Thus, the primary goal is to evaluate the effect of sirolimus on progression of MSA, including autonomic, cerebellar and parkinsonian features as measured by the UMSARS, a relevant clinical measure of disease progression. Secondary goals are to determine if there is any effect on neuroimaging (brain MRI) and ophthalmological (retinal OCT) biomarkers of the disease. As exploratory aim we will determine if there are any changes in plasma α Syn exosomes, as surrogate markers of autophagy.

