4.2 SCIENTIFIC RATIONALE FOR STUDY DESIGN

To determine whether to test sirolimus in a large phase 3 trial, we propose to conduct a clinical trial of sirolimus in MSA using a futility design. This approach minimizes the number of subjects and resources required for the study and provides an indication of whether or not to pursue larger and more definite studies. A futility design (60) is highly appropriate for MSA given: a) the low prevalence of the disease; b) the availability of historical controls from recent large studies (8, 39); and c) the availability of sensitive outcome measures. A futility design under the null hypothesis assumes that sirolimus will slow the progression of the disease, whereas the alternative hypothesis assumes no benefit of sirolimus. If the null hypothesis is rejected (i.e., futility of sirolimus to slow progression of MSA), a major phase III study will be discouraged, whereas non-futility will offer strong support for a phase III trial to detect clinical efficacy.

This study will also include a placebo group in 3:1 proportion. Our reason for including a placebo arm is to facilitate blinding to treatment assignment and also to permit a descriptive assessment of the validity of the assumed change in UMSARS over time in the historical control group; it will not be used as a basis of comparison for the active treatment arm.

This placebo-controlled futility design comparing outcome measures to historical controls has been used in other neurodegenerative disorders (61-63).

The study population (n=42 active agent, n=14 placebo) was selected based on power analysis calculation using the known annual progression of the UMSARS total score from published natural history studies (8, 39) and the progression in the placebo group of previous clinical trials of MSA(40), as well as from the minimally clinically significant difference in UMSARS (38) (see statistical section).

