5.5 STRATEGIES FOR RECRUITMENT AND RETENTION

Patients with MSA will be recruited from those that we are currently following at the NYU Dysautonomia Center. Our Center currently follows approximately 100 patients with MSA. In addition, we are in close contact with MSA patients advocacy groups (e.g. *Multiple System Atrophy Coalition*) and will collaborate closely with them in order to disseminate information about the trial and increase the likelihood of recruitment, by means of e-mail blast or letter. The recruitment e-mail/letter to be sent to patients with MSA is attached as an appendix. Any recruitment e-mail or letter to be used in this trial will be submitted to the IRB for approval prior to use.

We expect to screen an average of 8 patients per month and accruing an average of 3 patients per month. At this predicted rate, we expect to complete enrollment of the subjects (n=56) within 24 months with patients recruited only at the NYU Dysautonomia Center. A special effort will be made to include women and minorities.

A screening and enrollment log to record the consent and screening of all subjects and the outcome of each screening will be maintained. The log will provide a comprehensive list of all subjects who were screened for eligibility as well as consented, including the screened failures, the reasons for ineligibility, and reasons for nonparticipation of eligible subjects. This information will be collected centrally, will be included in the Essential Documents Binder, and will be used to enhance subject recruitment efforts.

The principal investigators or co-investigators will approach patients with MSA during a routine clinic visit to inquire whether they would be interested in being enrolled in this clinical trial. If so, patients will be given the consent form. The subject and family will be given enough time to read the informed consent in a quiet room to maintain privacy. The principal investigators, co-investigator or clinical study manager will explain the design of the study, discuss it with the patient and answer any questions or concerns. If the patient is satisfied by the responses of the investigators, the principal investigator will ask the patient to sign the consent form before entering the study. The original signed form will be kept within the study files, and the patient and family will be given a copy.

Screening procedures will include demography, medical history, inclusion and exclusion criteria

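### Section 9.4.5 stops the trial for overwhelming efficacy on an untested active-arm mean of 4 points or less, a conclusion the futility design cannot reach

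*Combined protocol and SAP*

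**What the plan says.** Section 9.4.5 sets the timing: "Interim efficacy analysis will be performed when 24 patients have completed the trial". If either of two criteria is met, "the trial will be stopped for overwhelming efficacy". The first criterion is "The average increase in the total UMSARS score is 4 points or less from baseline to week 48 in patients taking active agent", with no test, interval or significance level. The second, joined by OR, is that the increase in patients "taking active agent is significantly lower than in patients taking placebo", at P<0.001. The same section has two futility criteria. One is a raw mean ("The average increase in the total UMSARS score is at least 7 points or more from baseline to week 48"). The other is again a comparison with placebo at P<0.001.

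Elsewhere the design is narrower. The null hypothesis in sections 9.1 and 9.2 is a mean increase of at most 4.6 points, which is the historical 8.6 minus a promising difference of 4. Rejecting it means futility. Section 4.1 states the other outcome: "If the null hypothesis is not rejected, sirolimus would be considered for a phase 3 clinical trial". The synopsis and sections 4.1 and 4.2 leave clinical efficacy to that phase III trial. Of the placebo arm, section 4.2 says "it will not be used as a basis of comparison for the active treatment arm". Section 4.1 likewise rules it out for the primary outcome, and section 9.2 directs the primary and secondary efficacy comparisons to historical controls.

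**The concern.** The interim can announce more than the completed trial could. The best final result is failure to reject futility, which supports a further trial. Yet at 24 completers the plan provides for a stop labelled overwhelming efficacy, and as worded that stop is mandatory.

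The first trigger lies only 0.6 points below 4.6, the value at which sirolimus counts as merely promising. It is a bare mean from a small arm with no concurrent control. The second trigger uses the placebo arm in a way that three other sections exclude.

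At stake are an efficacy conclusion that the data could not carry and the planned one-sample analysis on 38 evaluable sirolimus patients, which an early stop would forgo.

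**Working it through.** **Inputs.** Historical increase 8.6, SD 9.2, promising value 4.6, one-sided alpha 0.05, 38 evaluable in the active arm, 10% dropout (section 9.2). Interim at 24 completers, trigger at 4 or less (9.4.5). Allocation 3:1 (section 5). Accrual as in section 5.5: "We expect to screen an average of 8 patients per month and accruing an average of 3 patients per month", with enrolment of 56 complete within 24 months. The split at the interim is not stated. I assume 24 × 3/4 = 18 sirolimus and 6 placebo.

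**The plan's own figures.** The plan gives no operating characteristics for the interim rule, so there is none to reproduce. The pooled historical mean does reproduce: (96 × 7.5 + 50 × 10.8)/146 = 8.63. The weighted SD is (96 × 8.4 + 50 × 10.7)/146 = 9.19.

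**Raw-mean trigger.** SE = 9.2/√18 = 2.17, and P(mean ≤ 4) = Φ((4 − μ)/2.17).

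| True mean increase | Meaning | P(stop) |
|---|---|---|
| 4.6 | exactly the promising value | Φ(−0.277) = 39.1% |
| 6.6 | 2-point benefit, below the 3.5-point MCID | Φ(−1.199) = 11.5% |
| 8.6 | no benefit | Φ(−2.121) = 1.7% |

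Simulation gives 39.0% for the first row. Over 14 to 24 sirolimus completers and SDs of 8.4 to 10.7 (the two historical SDs), that row ranges from 36% to 42%.

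**Evidence at the boundary.** For an observed mean of 4.0 with 18 patients and SD 9.2:

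- two-sided 95% CI: 4.0 ± 2.110 × 2.17 = −0.6 to 8.6 (8.575 before rounding);
- one-sided 95% upper limit: 4.0 + 1.740 × 2.17 = 7.8;
- test against 8.6: t = −4.6/2.17 = −2.12 on 17 df, one-sided p = 0.024 (two-sided 0.049).

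The alternative trigger for the same label requires P<0.001.

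**Placebo trigger.** SE of the difference = 9.2 × √(1/18 + 1/6) = 4.34. At P<0.001 with 22 df, the observed difference must be about 3.505 × 4.34 = 15.2 points (one-sided) or 3.792 × 4.34 = 16.4 (two-sided). Power for a true 4-point difference is 1.2% or 0.7%.

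**Effect on the final decision.** I simulated 38 sirolimus patients with the interim on the first 18 and a final one-sided t-test against 4.6. The probability that the efficacy stop fires and the completed trial would have declared futility is about 0.05% at a true mean of 4.6, and about 0.24% at both 6.6 and 8.6. Section 9.4.2 also contains a point-estimate rule. If that governs, the figures are about 8%, 7% and 1.5%.

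**Enrolment saved.** Section 4.4 defines completion as the last scheduled visit, which the Schedule of Activities puts at Day 365 (12 months).

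- At 3 per month, all 56 are enrolled at 56/3 = 18.7 months. The trigger falls at 24/3 + 12 = 20.0 months, or (24/0.9)/3 + 12 = 20.9 months with 10% dropout. Nothing is saved.
- At the 24-month pace (56/24 = 2.33 per month), the trigger falls at 24/2.33 + 12 = 22.3 months, or 23.4 with dropout. By then 52 to 55 of the 56 are enrolled.

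**The case against.** The strongest reply is that the rule does little damage to the decision the trial exists to make. A mean of 4.6 is the value the plan wants to carry forward, so stopping there advances a drug that would normally have advanced anyway. An inert drug meets the stop only 1.7% of the time but would escape futility at the final t-test about 16% of the time, so the interim route is the stricter one. This stands. A reader might take 39% as a false-positive rate, or infer that the stop would often wave through a futile drug. Neither follows from the plan's figures under the t-test. Under the point-estimate rule in 9.4.2 disagreement is larger, but it is still 8% or less.

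The boundary evidence is also not nil. On the plan's one-sided footing, a mean of 4.0 excludes 8.6 (upper limit 7.8). It remains far weaker than P<0.001, and it treats the historical 8.6 as known, although that value pools means of 7.5 and 10.8.

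A reader might also infer that patients still in follow-up would lose all their data. The documents do not say so. Section 9.4.5 is silent on those patients. The early-termination visit in section 4.1 collects UMSARS, MRI, OCT and exosome samples, and the synopsis allows the last available date. Those provisions address individual discontinuation, so what happens after a trial-wide stop is open. What would be forgone is the planned 38-patient analysis at week 48.

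**Conclusion.** The point holds as a conflict within the plan that needs correction. Section 9.4.5 requires a stop under a label that the objective, the hypotheses and the stated role of placebo do not allow. The raw-mean trigger would apply that label about 39% of the time (36% to 42% over plausible inputs) to a drug that is only at the promising value. The placebo trigger has about 1% power for a 4-point effect, so it adds almost nothing except a contradiction with sections 4.1, 4.2 and 9.2.

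The harm lies in the unsupported conclusion and the forgone analysis, not in a frequently wrong futility decision. In return the stop saves no enrolment at 3 per month and at most about 4 of 56 patients at the 24-month pace. These figures rest on the inferred 18:6 split, normally distributed changes with SD 9.2, and completion at Day 365.

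**What to change.** Delete both efficacy-stop bullets from section 9.4.5. State that the interim draws no efficacy conclusion, so that futile and not futile remain the only conclusions. Reconcile the remaining futility bullet, which compares active with placebo at P<0.001, with sections 4.1, 4.2 and 9.2. The safety stopping provisions in 10.1.2 and the withdrawal provisions in 7.2 are outside this point and need no change for it.

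The cost is about one paragraph of protocol wording. The option of an early efficacy stop is given up, but on the plan's own accrual figures it would come when enrolment is complete or nearly so.
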